1.3.2 Sample Size

A total of 400 subjects will be enrolled in this study; 200 participants will enroll in the control arm and 200 will enroll in the intervention arm. Within these two arms, 100 subjects will be "patients" and "support persons." "Patients" are defined as people who will receive an in-clinic abortion on the day of their participation. "Support persons" are the individuals whom the patient chooses to accompany them during the in-clinic abortion procedure. Support persons will only actually accompany patients in the in-clinic procedure room if they are randomized to the

intervention arm of this study. Health care providers will also be invited to participate in this research study—and enrollment numbers will depend upon the amount of unduplicated staff who will perform or assist with the D&C procedure on days when enrollment will occur. "Health care providers" include the physician performing the abortion and nurses assisting the physician within the abortion procedure room.

Prior studies indicate a 20mm difference in VAS is clinically significant and that the common standard deviation for VAS scores is 23 mm [8]. Based on these assumptions, a sample size of 28 with 14 women in each arm will have 90% power to detect at least a 20mm difference between the change in pain score from baseline, to during the procedure, to after the procedure between the two groups, using a Student's t-test evaluated at the 2-sided 0.05 significance level.

We have chosen a larger sample size to also provide a representative sample of our patient population for our secondary aims of patient and support person satisfaction as well as nurse and physician satisfaction. This sample size was calculated based on the total number of in-clinic abortion patients seen in the Tampa Health Center in 2015 with a Confidence Level of 95% and a Confidence interval of 10.

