1.3.11 Data Analysis

Analysis will be performed using Qualtrics statistical software. Analyses will be performed on all control and experimental group data. The control group is defined as the standard care without presence of support person, whereas the intervention group is all those receiving standard care with the presence of a support person in the procedure room. Demographic, behavioral, and clinical characteristics will be compared between the two arms using frequency tests, Student's ttest, chi-squared tests, and two-way ANOVA, where appropriate. The change in pain score, as assessed by VAS, from baseline to recovery room will be compared within each group using paired Student's t-test if the data are normally distributed or Wilcoxon signed-rank test if the data do not follow a Gaussian distribution. Similarly, the difference in the change in VAS scores between the

study arms will be compared using Student's t- or Mann-Whitney U tests, where appropriate. Questionnaire answers will be compared between both arms of the study using chi-squared statistical analysis. Statistical analysis will be performed by both the Principal Investigator and statistician.

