1.7 Expected outcomes of the study and dissemination of findings

This study aims to evaluate pain and anxiety levels in patients undergoing in-clinic abortion as well as assess provider and support person satisfaction when support person is in procedure room compared to when support person not in the procedure room. If this study demonstrates that having a support person in the room decreases pain and/or anxiety, this may help to support the inclusion of a support person in the procedure room and improve patient experience. In addition, if providers have a good experience, it may help allay provider concerns about having a support person in the room.

The final results will be presented at a national conference and submitted for publication in a peer-reviewed journal.

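### The observed distribution decides whether pain is compared by t-test or rank test, and both ignore randomisation by day; one pre-specified mean difference in mm should replace the switch

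*Protocol*

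**What the plan says.** Protocol 1.3.2 (Sample Size) sets the benchmark, "Prior studies indicate a 20mm difference in VAS is clinically significant", and adds that "the common standard deviation for VAS scores is 23 mm". From these it concludes that "a sample size of 28 with 14 women in each arm will have 90% power to detect at least a 20mm difference", "using a Student's t-test evaluated at the 2-sided 0.05 significance level". It then enrols many more people: "200 participants will enroll in the control arm and 200 will enroll in the intervention arm". Section 1.3.8 requires enrolment in patient and support-person pairs, so this means 100 patients per arm. The stated reason is a representative sample for the satisfaction aims.

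Protocol 1.3.11 (Data Analysis) compares the change from baseline to recovery room within each arm by a paired t-test "if the data are normally distributed or Wilcoxon signed-rank test if the data do not follow a Gaussian distribution". The next sentence treats the between-arm comparison in the same manner, by Student's t or Mann-Whitney U as suits. The 20 mm figure is not mentioned there.

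Protocol 1.3.1 randomises procedure days, not patients, by drawing slips from an envelope holding five for each arm. Section 1.7 describes the hoped-for outcome as "If this study demonstrates that having a support person in the room decreases pain and/or anxiety", which it says may help support the practice.

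**The concern.** Three features of the stated analysis combine badly.

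- **The test depends on the data.** The choice is made after the data are seen, and no criterion for normality is given. The two branches also address different quantities: a difference in means, and an ordering of ranks.
- **The tests assume independent patients.** Patients treated on the same day share an allocation and probably staff and conditions. If outcomes within a day are correlated, both tests overstate precision.
- **The result is not tied to the benchmark.** The protocol gives a clinical yardstick in mm, but the rank branch ends in a p-value with no value in mm. With 100 patients per arm, significance says little about whether an effect is close to 20 mm.

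At stake is how the headline pain result can be read. A small reduction and one of clinically significant size could both appear simply as a significant decrease.

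**Working it through.** **Inputs from the protocol (1.3.2, 1.3.8):** benchmark 20 mm; SD 23 mm; two-sided alpha 0.05; 100 patients per arm.

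**The plan's own figure.** For two arms and 90% power, n per arm = 2 × [23 × (1.96 + 1.2816) / 20]² = 27.8. That is 28 per arm, or 29 with the exact t-test. The stated 14 per arm does not reproduce and has about 60% power under the t-test. The value 14 matches the one-sample formula, [23 × 3.2416 / 20]² = 13.9. This is a separate matter: 100 per arm exceeds 29, so it does not drive the present point.

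**Smallest significant observed difference, patients independent, as 1.3.11 plans:**

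t(0.975, 198) × SD × √(2/100) = 1.972 × 23 × 0.1414 = **6.4 mm**, about a third of 20 mm.

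**Sensitivity to the SD.** The protocol gives 23 mm for VAS scores but applies it to a change. If 23 mm is the SD of a single score and ρ is the correlation between the two scores, the SD of change is 23 × √(2(1 − ρ)).

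| ρ (assumed) | SD of change (mm) | Threshold (mm) |
|---|---|---|
| 0.75 | 16.3 | 4.5 |
| 0.5 | 23.0 | 6.4 |
| 0.25 | 28.2 | 7.9 |
| 0 | 32.5 | 9.1 |

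If the awkward sentence in 1.3.2 meant 100 patients in total (50 per arm), the threshold at SD 23 mm would be 9.1 mm.

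**Sensitivity to clustering by day.** The protocol states no ICC and no number of patients per day, so both are assumed: m = 5 to 10 patients per day and ICC 0.01 to 0.10. With design effect DE = 1 + (m − 1) × ICC and k = 200/m days, the threshold is t(0.975, k − 2) × 23 × √(0.02 × DE).

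| m | ICC | DE | Threshold (mm) |
|---|---|---|---|
| 5 | 0.01 | 1.04 | 6.7 |
| 5 | 0.05 | 1.20 | 7.2 |
| 5 | 0.10 | 1.40 | 7.8 |
| 10 | 0.01 | 1.09 | 7.1 |
| 10 | 0.05 | 1.45 | 8.2 |
| 10 | 0.10 | 1.90 | 9.4 |

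Ignoring days makes the standard error too small by a factor √DE, here 1.02 to 1.38. Combining the most clustered row with an SD of change of 32.5 mm gives 9.42 × √2 = 13.3 mm.

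**What a p-value would hide.** At SD 23 mm with independent patients, an observed 7 mm has a 95% CI of 7 ± 6.4, or 0.6 to 13.4 mm. That is significant, yet the whole interval lies below 20 mm. At SD 32.5 mm the same 7 mm gives 7 ± 9.1, or −2.1 to 16.1 mm, which is not significant. At SD 23 mm the trial has 86% power for a true 10 mm, half the benchmark.

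**The case against.** Much of the opposing case stands.

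- **Estimates and intervals are often left to the SAP.** One may exist here. Their absence from a protocol is not a fault, and 1.3.11 does not say that only p-values will be reported.
- **A rank test does not prevent reporting in mm.** Pain is marked on a 100 mm line, and means, medians or a shift estimate could accompany Mann-Whitney. A reader might infer that no difference in mm can be produced on that branch. The text supports only that the named test does not itself supply one.
- **Significance below the planning difference is normal.** Even 29 per arm would be significant from about 12 mm: 2.003 × 23 × √(2/29) = 12.1. A reader might infer that the trial is wrongly oversized, but 1.3.2 justifies the larger sample.
- **Section 1.7 is hedged.** A reader might take it as a rule to change practice on any significant decrease. It says only that such a finding may help support the practice.
- **Skewed data are not documented.** Recovery-room pain may gather near zero, but the tested quantity is a change from expected pain, which need not.
- **The normality rule is explicit only for the within-arm test.** It reaches the between-arm test by the analogy between the two sentences.

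These points do not answer what the protocol does fix: a data-driven choice of test, two tests that both ignore the randomised unit, and a benchmark in mm that the analysis section does not use.

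**Conclusion.** The point holds as a weakness in the stated method. It is not evidence that the trial is mis-sized or that a significant result below 20 mm would be wrong. Section 1.3.11 lets the observed distribution choose the pain test, treats patients as independent despite randomisation by day, and on one branch uses a test that gives no difference in mm.

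On the protocol's inputs, with 23 mm taken as the SD of change, significance begins at about 6.4 mm. It begins at about 9.1 mm if the two scores are uncorrelated, and at up to about 13 mm under the heaviest assumed clustering as well. All of these lie below 20 mm, so it is safe to conclude that a p-value alone does not locate the effect relative to the benchmark. The exact threshold is not safe: it depends on the correlation between scores, the ICC and the number of patients per day, none of which the protocol gives.

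**What to change.** In 1.3.11, replace the choice between t and rank tests with one primary between-arm pain analysis named in advance. This would be the mean difference in VAS change in mm with a 95% CI, from a model that accounts for procedure day, with a small-sample correction if days are few. The number of days matters because it, more than the 100 patients per arm, governs how far large-sample arguments about non-normal data can be relied on. Keep Mann-Whitney as a sensitivity analysis only. When the pain result is described, report the interval alongside the 20 mm from 1.3.2, so that a significant effect smaller than that is seen as such.

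The cost is modest. Procedure day must be kept in the dataset, someone must fit a clustered model (whether the software named in 1.3.11 can do so needs checking), and the interval will probably be wider. Enrolment, procedures and questionnaires do not change.

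### The stated 28 women (14 per arm) give about 60% power, not 90%, on the protocol's own inputs; 29 per arm (58 in total) are needed.

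*Protocol*

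**What the plan says.** Section 1.3.2 (Sample Size) of the protocol gives a complete power calculation for the VAS pain outcome, which is a primary aim in section 1.1.2.

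- Target difference: "Prior studies indicate a 20mm difference in VAS is clinically significant".
- Variability: "the common standard deviation for VAS scores is 23 mm".
- Test: "using a Student's t-test evaluated at the 2-sided 0.05 significance level".
- Quantity compared: "difference between the change in pain score from baseline, to during the procedure, to after the procedure between the two groups".
- Result: "a sample size of 28 with 14 women in each arm will have 90% power to detect at least a 20mm difference".

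The same section then plans 400 subjects, 200 per arm. With patients enrolled in pairs with a support person, this reads as 100 patients per arm. The larger number is justified by the satisfaction aims and by the clinic's 2015 patient volume, not by the pain comparison.

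**The concern.** A 20 mm difference with an SD of 23 mm is a standardised difference of 0.87. That is large, but not large enough for 14 per arm to give 90% power in a two-sample test. Nothing is left open that a statistical analysis plan would settle, because effect, SD, test, significance level, power and answer are all written down.

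There is a second difficulty. The 23 mm is given for VAS scores, but the test is on change in VAS. The SD of a change depends on the correlation between baseline and follow-up, which is not stated.

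This is the protocol's only power statement. Because the larger enrolment is justified on other grounds, 28 women stand as the declared requirement for the pain aim. If recruitment, scheduled for three months in the section 5 timeline, fell short, 14 per arm could wrongly be taken as enough. The figure could also be carried into the publication.

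**Working it through.** **Inputs (all from section 1.3.2).** Difference δ = 20 mm; SD σ = 23 mm; two-sided α = 0.05; target power 0.90; two-sample Student's t-test; equal arms; no dropout allowance. Standardised difference d = 20/23 = 0.870.

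**1. The plan's own figure, 14 per arm.** Power comes from the noncentral t distribution with 2n − 2 degrees of freedom and noncentrality d·√(n/2).

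- n = 14: noncentrality 0.870 × √7 = 2.30, critical value 2.056 on 26 df, power **60.1%** (63.3% by the normal approximation). The stated 90% is not reproduced.
- With 14 per arm, 90% power needs a difference of 29.3 mm at SD 23 mm, or an SD of 15.7 mm at a difference of 20 mm.

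**2. The number needed for 90%.**

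- Normal approximation: n = 2(1.96 + 1.2816)²/d² = 27.8, so 28 per arm.
- t-test: n = 28.8, so **29 per arm, 58 in total**. Power is 89.2% at 28 per arm and 90.2% at 29.

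**3. Other readings of the stated inputs.**

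| Variant | Result |
|---|---|
| One-sided 0.05, 14 per arm | 72.4% power |
| One-sided 0.05, 90% power | 24 per arm |
| Two-sided 0.05, 80% power | 22 per arm |
| One-sample normal formula, (1.96 + 1.2816)²/d² | 13.9, rounded up to 14 |
| Exact paired or one-sample t-test, 90% power | 16 |

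No standard two-arm variant gives 90% power with 28 in total. The one-sample normal formula does produce 14, but it is not the between-group test that the protocol names. Half of 27.8 is also 13.9, so the document cannot show which slip was made.

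**4. SD of a score versus SD of a change.** If 23 mm is the SD of a single score and is the same at both times (an assumption), the SD of the change is 23·√(2(1 − r)), where r is the baseline-to-follow-up correlation. The protocol gives no r, so a range is shown.

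| r (assumed) | SD of change, mm | Power at 14 per arm |
|---|---|---|
| 0 | 32.5 | 34.7% |
| 0.3 | 27.2 | 46.5% |
| 0.5 | 23.0 | 60.1% |
| 0.7 | 17.8 | 81.6% |
| 0.75 | 16.3 | 87.9% |
| 0.8 | 14.5 | 93.8% |

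At r = 0.3, 90% power needs 40 per arm. The stated 14 per arm reaches 90% only when the SD of change is 15.7 mm, that is r = 1 − (15.7/23)²/2 = 0.77.

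**5. What 100 patients per arm can detect with 90% power.**

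- SD 23 mm, independent patients: 10.6 mm. Power for 20 mm exceeds 99.9%.
- SD 32.5 mm (r = 0), independent patients: power for 20 mm is 99.1%.
- Section 1.3.1 randomizes procedure days, not patients, so a design effect applies. The protocol gives neither patients per day nor an intraclass correlation. Taking design effects of 1.33 to 2.44 purely as assumptions, the effective number per arm is 100/1.33 = 75 to 100/2.44 = 41. The detectable difference then runs from 12.2 mm (r = 0.5, design effect 1.33) to 19.7 mm (r = 0.3, design effect 2.44).

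**The case against.** The strongest reply is that the error changes nothing in the trial. Twenty-eight women were never going to be the sample. At 100 patients per arm, power for 20 mm stays just above 90% even with a change SD of 27.2 mm and a design effect of 2.44. This stands, and it is why the matter is a correction of the text and not a call for more patients. It does not make the sentence true.

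A second reply is that 23 mm is literally the SD of a score, so a high enough correlation would rescue the figure. The arithmetic is right: r of about 0.77 gives 90% power at 14 per arm. But the protocol states no correlation and applies 23 mm directly. Its baseline is the pain the patient expects, while the later ratings are of pain felt (sections 1.3.8.1 and 4.4), so a correlation that high is doubtful and would have to be justified.

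Two further points are fair. How the 28 arose cannot be known from the document. The design effects are assumptions without a source, so the 12.2 to 19.7 mm range is illustrative. Neither point touches the core result.

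**Conclusion.** The power statement is wrong as written. On the protocol's own inputs, 14 women per arm give 60.1% power, and 90% needs 29 per arm, about twice the stated number. This rests only on the figures in section 1.3.2 and assumes independent patients; clustering by day would raise the requirement. Using the SD of scores for a comparison of changes adds uncertainty, mostly unfavourable unless the correlation is above 0.5.

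The consequence is limited. With 100 patients per arm the pain comparison keeps at least 90% power for 20 mm at SD 23 mm, and also across the range of correlation 0.3 to 0.5 and design effect 1.33 to 2.44. The sentence should be corrected because it is the sole stated basis for power on a primary aim.

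**What to change.** In section 1.3.2, replace the sentence with one saying that 29 women per arm (58 in total) give 90% power to detect 20 mm at an SD of 23 mm with a two-sided 5% two-sample t-test, before any allowance for clustering by procedure day.

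Then add what the planned 100 patients per arm can detect. Use an SD for the variable actually analysed: either a sourced SD of change, or 23 mm with a stated correlation and a range around it. Apply a design effect for procedure day, with the assumed patients per day and intraclass correlation written out.

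The cost is a text amendment. No extra patients are needed, since the planned enrolment already exceeds the corrected number.

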1.1.2 Hypotheses and Objectives

Hypotheses:

Social support in the abortion procedure room will decrease perceived pain and anxiety levels and increase satisfaction for the patient.

- 1. Social support in the procedure room influenced the patient's health outcomes in the following areas:
 - 1. Decreased pain
 - 2. Decreased anxiety
 - 3. Increased patient satisfaction
- 2. The social support person will report that they were able to give effective support to the patient.
- 3. The physician and the nurse will find the support person effective in supporting the patient.

Null Hypothesis:

- 1. Social support in the abortion procedure room will not change patient levels of perceived pain, anxiety, or satisfaction.
- 2. The social support person will report they did not give adequate support.
- 3. The health care provider and the surgical assistant will not find the support person effective

in supporting the patient.

Objectives

Primary Aims:

- To assess a change in expected pain level from baseline, immediately after the procedure, and again ten minutes after arrival to the recovery room as determined by a 100mm visual analog scale (VAS) for patients with in-room social support during the procedure as compared to those who do not.
- To assess pre- and post-procedure state anxiety levels as determined by the 20-question State-Trait Anxiety Inventory (STAI) for patients with in-room social support as compared to patients without in-room social support.

Secondary Aims:

- To measure acceptability and effectiveness of having social support in the procedure room as reported by the surgical assistant and healthcare providers as determined by a post-procedure questionnaire.
- To evaluate if support was effectively given to the patient as reported by the support person as determined by a post-procedure questionnaire.

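### Support-person and staff satisfaction is called a secondary aim (1.3.2) and promised as a with-versus-without comparison (1.7), but forms 4.5 to 4.8 never ask it and 1.1.2 lists other constructs

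*Protocol*

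**What the plan says.** Three parts of the protocol describe the support-person and staff outcomes.

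- Section 1.3.2 gives the reason for going beyond the pain calculation: "We have chosen a larger sample size to also provide a representative sample of our patient population". The outcomes that the larger sample is meant to serve are named there as "our secondary aims of patient and support person satisfaction as well as nurse and physician satisfaction".
- Section 1.7 states the comparison. The study is to "assess provider and support person satisfaction when support person is in procedure room compared to when support person not in the procedure room".
- Section 1.1.2 lists the aims. The primary aims are VAS pain and STAI anxiety. The secondary aim for staff is "To measure acceptability and effectiveness of having social support in the procedure room as reported by the surgical assistant and healthcare providers", and the one for support persons is whether they gave the patient effective support. Satisfaction is in no listed aim. Patient satisfaction appears in the hypotheses of the same section.

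Section 4 contains the questionnaires: 4.2 and 4.3 for patients, 4.5 and 4.6 for support persons, 4.7 and 4.8 for staff, each pair giving the intervention and then the control version. Section 1.3.11 plans chi-squared comparisons of questionnaire answers between the arms.

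**The concern.** The outcome named in 1.3.2 and 1.7 is not the outcome listed in 1.1.2, and the forms follow 1.1.2. If the forms are used as shown, there will be no satisfaction answer from any support person, nurse or physician in either arm. The team would then have to choose afterwards which comfort, helpfulness or willingness item to report as satisfaction. Most of those items are also worded differently in the two arms, so the planned test would set an account of what happened against a guess about what might have happened. An analysis plan can define how answers are analysed, but it cannot supply an answer to a question that was not put.

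**Working it through.** **Step 1. Promise, aim and item for each group.**

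| Group | 1.3.2 | 1.7 | Aims in 1.1.2 | Satisfaction item on the forms |
|---|---|---|---|---|
| Patient | satisfaction | pain and anxiety | pain, anxiety; satisfaction only as a hypothesis | item 1 of 4.2 and 4.3, same wording and options |
| Support person | satisfaction | satisfaction, compared | support given | none on 4.5 or 4.6 |
| Nurse, physician | satisfaction | provider satisfaction, compared | acceptability, effectiveness | none on 4.7 or 4.8 |

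Of the four satisfaction outcomes in 1.3.2, one has an item and three have none.

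**Step 2. What forms 4.5 to 4.8 do ask.** The support-person forms cover role clarity, effectiveness, whether the patient was comforted and the person's own comfort. Form 4.5 adds reasons for discomfort and willingness to serve again. The staff forms cover helpfulness to self and to the patient, discomfort, concerns, having to support the support person, making accompaniment permanent, MVA and complications. Several of these come near to satisfaction. The protocol names none of them as its measure.

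**Step 3. Are the shared items the same question in both arms?** Leave aside free-text comments and the two factual items (MVA, complications).

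- Support person, items 1 to 4: 4 pairs. All 4 ask about the actual role or experience on 4.5 and a hypothetical one on 4.6.
- Staff, items 1 to 6: 6 pairs. Items 1 to 5 ask what happened on 4.7 and what would have happened on 4.8. Item 6 (permanent arrangement) is worded alike as far as the text shows, but 4.7 offers a no-opinion option that 4.8, as shown, does not.
- Total: 4 + 6 = 10 pairs, of which 4 + 5 = 9 set experience against hypothesis. The remaining one is an opinion on policy.
- Willingness to serve again has no counterpart on 4.6.

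A chi-squared test on one of the nine pairs mixes two things: any effect of accompaniment, and the difference between judging an event and imagining one. It could show a difference when both arms are equally satisfied with the day, or hide one when they are not.

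**Step 4. Does the enlarged sample lose its basis?** The inputs in 1.3.2 are "with a Confidence Level of 95% and a Confidence interval of 10" and "the total number of in-clinic abortion patients seen in the Tampa Health Center in 2015" (number not given). "A total of 400 subjects will be enrolled in this study" is read here as 100 patients and 100 support persons per arm. Assume a proportion of 0.5 and read the interval as ±10 percentage points:

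- n0 = 1.96² × 0.25 / 0.10² = 96.04, so 97 without a finite-population correction.
- With the correction, n = n0 / (1 + (n0 − 1)/N) gives 73 (N = 300), 81 (500), 88 (1,000), 92 (2,000) and 95 (5,000).
- With 100 per arm, the half-width is 1.96 × √(0.25/100) = 0.098, or ±9.8 points.

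So 100 patients per arm is compatible with the stated precision, though it cannot be confirmed without the 2015 volume. If the interval means a total width of 10 (±5 points), n runs from 169 (N = 300) to 385 (no correction).

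The formula serves any questionnaire proportion, including patient satisfaction, which is measured. For support persons the numbers are there and the item is missing. For staff it fixes nothing, because "enrollment numbers will depend upon the amount of unduplicated staff". With an assumed 5, 10 or 15 staff and one answer each, 1.96 × √(0.25/n) gives about ±44, ±31 or ±25 points. All these figures treat answers as independent, although allocation is by procedure day.

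**The case against.** The strongest reply is that this is loose labelling of a concept that is measured. The title concerns satisfaction with having a support person in the room, the summary repeatedly couples experience with satisfaction, and 1.7 goes on to speak of providers having a good experience. Comfort, helpfulness, willingness to serve again and support for a permanent arrangement all bear on that, and an analysis plan not shown here could name one as the measure.

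Part of this stands. It would be wrong to say that nothing relevant is collected from support persons and staff; acceptability and effectiveness, as listed in 1.1.2, are covered. What the reply does not meet is the comparison in 1.7. Naming a proxy later would not make an experienced and a hypothetical question the same question, and the one staff item worded alike asks about policy.

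A reader might also infer four stronger things that the documents do not support.

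- That patient satisfaction has no place among the endpoints. It is in hypothesis 1, is called a secondary aim in 1.3.2, is asked identically in both arms and falls under the chi-squared comparison in 1.3.11. Only its entry in the 1.1.2 list is missing.
- That the enlarged sample rests on unmeasured outcomes alone. The precision calculation also serves the patient satisfaction item.
- That the title and 1.3.2 also promise a comparison of support-person and staff satisfaction. Only 1.7 states one.
- That nurse and physician answers cannot be separated because the staff forms show no role field. Section 1.3.8.3 calls the attached forms a sample, and staff consent individually, so role may be recorded elsewhere.

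**Conclusion.** The point holds as a mismatch between promise, aims and instruments. Three of the four satisfaction outcomes in 1.3.2 have no item on any form, and the comparison in 1.7 cannot be obtained from forms 4.5 to 4.8, because nine of their ten shared opinion items pair experience with a hypothetical and none is designated as satisfaction. Patient satisfaction needs only a line in 1.1.2. The VAS pain and STAI anxiety comparisons are not affected, and this point gives no reason to change the sample size. It should be corrected before the forms are used. The conclusion assumes that the forms in use match section 4 as shown; the item count depends on that, but the disagreement between 1.1.2, 1.3.2 and 1.7 does not.

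**What to change.** Choose one of two routes.

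1. Keep the satisfaction comparison. Add to forms 4.5, 4.6, 4.7 and 4.8 one item with the same wording and response options in both arms. It could ask, for example, for overall satisfaction with the arrangement made for the support person at today's procedure, using the five options of item 1 on the patient forms. Such wording can be answered whether or not the support person was in the room, and it stays on accompaniment rather than the visit as a whole. Name it in 1.1.2 as the support-person and staff satisfaction outcome.
2. Drop the comparison. Reword the title, summary, 1.3.2 and 1.7 (and the project title in section 5) so that support-person and staff outcomes are acceptability and effectiveness. Report the experienced and hypothetical items descriptively by arm, and remove the satisfaction comparison for these two groups.

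On either route, add to 1.1.2 a secondary aim for patient satisfaction, measured by item 1 of forms 4.2 and 4.3 and compared between arms.

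The first route costs one question on four paper forms and a few seconds per form, which staff would repeat after each procedure. The second costs only text edits, but gives up an outcome named in the title.
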